6. SELECTION AND DISPOSITION OF STUDY POPULATION

6.1 Number of Subjects

A maximum 20 subjects to complete the study, in which 10 subjects with dermatologic procedure on the head/neck and 10 subjects with dermatologic procedure on the body.

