6.5.2. Prohibited Therapies

None other than as specified in the Inclusion/Exclusion criteria.

Protocol Version 1:

This document contains confidential, proprietary information.

Protocol GLI.04.US.SL.017

CONFIDENTIAL

The decision to administer a prohibited medication/treatment should be made with the safety of the subject being the primary consideration. Whenever possible, Galderma Laboratories, L.P. should be notified before the prohibited medication/treatment is administered to discuss possible alternatives.

If a subject receives prohibited therapy during the study, the subject may be allowed (at the discretion of the investigator / Galderma Laboratories, L.P.) to continue in the study for safety evaluation purposes, only.

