7.6 Treatments Compliance

Subjects will complete a daily diary, recording treatment product applications and comment during the study. Treatment product and diaries will be dispensed to subjects at Day 0 and reviewed for compliance at Day 28 visit. Treatment product will be visually inspected and weighed prior to distribution at Day 0 and at Day 28. Subjects will be instructed to return the treatment product and daily diary at Day 28 visit. If subjects do not return their treatment product or diary at the end of the study, a verbal confirmation will be obtained for usage compliance, and it will be documented as a note to file.

Any suspected noncompliance with the treatment product or study instructions will be addressed by the Investigator or clinic staff. The Investigator will determine whether a subject's noncompliance will affect the study outcome and whether the data should be excluded from statistical analyses.

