8.3.4. General Study Instructions

- Avoid extended periods of sun exposure for the duration of the study.
- Do not use any topical products (except sunscreen as needed) on the surgical site other than the provided treatment product for the duration of the study.

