10.1 Clinical Grading by Investigator

Investigator will perform clinical grading at the surgical site on each subject at baseline (pre- and post-procedure), day 7/14, and day 28. Investigator will grade the severity of wound parameters based on a visual analog scale, described in the table below (for erythema, edema, overall wound appearance, half-point scores can be used as necessary to better describe the condition):

Parameters	Score 0	Score 1	Score 2	Score 3
Erythema	None/absent	Mild	Moderate	Severe

Protocol Version 1:

This document contains confidential, proprietary information.

Edema	None/absent	Mild	Moderate	Severe
Overall wound appearance	Excellent (absent of wound)	Good (slightly visible wound)	Fair (moderately visible wound)	Poor (marked visible wound)

Parameters	Score 0	Score 1	Score 2	Score 3	Score 4
Scabbing/crusting	None	Slight (up to 30%)	Moderate (31-60%)	Extensive (61-90%)	Almost complete or complete (91-100%)

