10.2 Tolerability Assessments

Tolerability assessments will be performed by subjects at the surgical site at baseline (pre- and post-procedure), day 7/14, and day 28. Subjects will grade the degree of irritation parameters that they experience based on a 4-point analog scale, described in the table below (with half-point scores used as necessary to better describe the clinical condition):

Parameters	Score 0	Score 1	Score 2	Score 3
Burning	None	Mild	Moderate	Severe
Itching	None	Mild	Moderate	Severe
Pain	None	Mild	Moderate	Severe

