11. STATISTICAL ANALYSIS

A descriptive statistical summary will be provided for clinical grading and tolerability assessments. The descriptive summary will be performed for each parameter, including N, mean, median, standard deviations, minimum, and maximum of values at all applicable time points.

Mean of the change from baseline (pre-procedure) will be estimated at applicable post-baseline time point. The null hypothesis, that the mean change from baseline (pre-procedure) is zero, will be tested using methods described in the Statistical Analysis Plan table.

The following will be calculated and reported for each evaluation parameter at applicable post-baseline (pre-procedure) time point:

$$\text{Percent mean change from baseline} = \frac{(\text{postprocedure or visit mean score} - \text{baseline preprocedure mean score})}{\text{baseline preprocedure mean score}} \times 100$$

$$\text{Percent of subjects improved/worsened} = \frac{(\text{number of subjects improved/worsened from baseline preprocedure})}{\text{total number of subjects}} \times 100$$

Questionnaires will be tabulated, and the percentage of all response options (favorable and unfavorable) will be reported for each question and each timepoint.

Statistical Analysis Plan

Evaluation	Change from Baseline Pre-Procedure	Notes/Interpretation
Clinical grading	Paired t-test; If normality fails, a Wilcoxon signed-rank test will be used.	A decrease in scores indicates an improvement
Tolerability assessment	Paired t-test; If normality fails, a Wilcoxon signed-rank test will be used.	A decrease in scores or lack of significant increase indicates tolerability/safety of the treatment product
Self-assessment questionnaire	N/A	Percentage of favorable and unfavorable responses will be provided for each question.

All statistical tests will be 2-sided at significance level alpha = 0.05 unless specified otherwise. *P* values will be reported to 3 decimal places.

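### Section 7.6 lets the wound-grading role decide case by case whose noncompliant data are excluded, with no threshold and no masking from the grades, and Section 11 names no analysis set

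*Combined protocol and SAP*

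**What the plan says.** - **Who decides.** Section 7.6 leaves it to the Investigator to judge whether a subject's "noncompliance will affect the study outcome and whether the data should be excluded from statistical analyses". The evidence named is the diary, inspection and weighing of the product, and a verbal confirmation if either is not returned. No minimum number of applications, product weight or deadline is set.
- **Who grades.** Section 10.1: "Investigator will perform clinical grading at the surgical site on each subject". The tolerability scores are the subjects' own (Section 10.2: "Tolerability assessments will be performed by subjects at the surgical site").
- **When.** Sections 9.1.3 and 9.1.4 list the compliance review as step 3, after grading in step 2 of the same visit. Day 28 is the last grading visit.
- **What can count as noncompliance.** Section 7.6 covers study instructions as well as product use. Section 8.3.4 tells subjects to put nothing but sunscreen "on the surgical site other than the provided treatment product for the duration of the study".
- **What is analysed.** Section 11 names no analysis set. It divides the number improved or worsened by "total number of subjects" without saying who is counted. Section 6.1 gives only a completion target: "A maximum 20 subjects to complete the study".
- **How tolerability is read.** A decrease in scores, or a "lack of significant increase indicates tolerability/safety of the treatment product".
- **Prohibited therapy.** Under Section 6.5.2 such a subject may be allowed "to continue in the study for safety evaluation purposes, only". Section 11 does not take this up.

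**The concern.** When compliance is reviewed in the listed order, the grades for that visit already exist. The only ground given for exclusion is an effect on the study outcome, which points the decision-maker towards the outcome itself. No section describes masking, an independent grader or a separate reviewer of exclusions.

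Noncompliance can plausibly be linked to outcome: for example, a subject whose wound stings or heals slowly might turn to another product. That link is a conjecture, not something the documents state. If it occurs, excluding such subjects removes unfavourable results from a single-arm study of about 20 people. For tolerability, losing a significant increase produces the favourable conclusion directly. Because the denominator is undefined, two analysts could also follow Section 11 faithfully and report different percentages.

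**Working it through.** The plan gives no effect size, SD, dropout rate or expected number of exclusions, so there is no figure of its own to reproduce. From the documents come n = 20, two-sided alpha 0.05, and a paired t-test with Wilcoxon signed-rank if normality fails. All other inputs below are assumptions.

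**1. Tolerability, discrete example.** Suppose *m* of 20 subjects worsen by one point and the rest do not change. With zero changes dropped and all *m* changes in one direction, the exact Wilcoxon p is 2 × (1/2)^m.
- Start at m = 6: 2/64 = 0.031. After one worsened subject is excluded, m = 5: 2/32 = 0.063. Significance is lost with one exclusion.
- Start at m = 7: 2/128 = 0.016, then 0.031, then 0.063. Two exclusions are needed.

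The count depends on the version of the test, which Section 11 does not specify. From m = 6, excluding 0, 1, 2 or 3 worsened subjects gives:

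| Test | 0 | 1 | 2 | 3 |
|---|---|---|---|---|
| Exact Wilcoxon | 0.031 | 0.063 | 0.125 | 0.250 |
| Normal approximation, continuity-corrected | 0.020 | 0.037 | 0.072 | 0.149 |
| Normal approximation, uncorrected | 0.014 | 0.025 | 0.046 | 0.083 |
| t-test | 0.010 | 0.021 | 0.042 | 0.083 |

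Six ones and fourteen zeros clearly fail a normality check (Shapiro-Wilk p < 0.001), so under Section 11 the Wilcoxon rows would normally apply.

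**2. Tolerability, simulated.** Normal changes, true worsening 0.66 SD, n = 20, t-test, with the *k* worst subjects dropped. The chance of a significant increase is 0.80, 0.70, 0.59 and 0.48 for k = 0, 1, 2 and 3.

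**3. False improvement on the clinical grades.** Normal changes, true mean change from pre-procedure of zero, n = 20, t-test. The chance of a significant decrease is:
- no exclusion: 0.025;
- one random noncomplier, dropped only if worsened: 0.030;
- two such subjects: 0.037;
- the 1, 2 or 3 worst subjects always dropped: 0.075, 0.15, 0.26.

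If the true change is instead a rise of 0.5 SD, the chance stays below 0.001 with up to two of the worst dropped. If two subjects are removed at random under a zero true change, the two-sided error stays at 0.05.

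**4. Denominator.** Suppose 18 of 20 treated subjects are graded at a visit.
- 14 improved: 14/18 = 77.8%, against 14/20 = 70.0%.
- 4 worsened: 4/18 = 22.2%, against 4/20 = 20.0%.

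The graded denominator gives the higher percentage for both. That flatters improvement and is stricter on worsening, so neither choice is neutral and both counts should be shown.

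**The case against.** - **The plan is not without a criterion or evidence.** Section 7.6 names a ground and three sources of evidence. This stands; what is missing is an operational threshold and separation from the grades.
- **Grader and decider need not be one person.** The study is multi-center, and the documents show a shared role only. That they are the same individual at a site is the natural reading but is not stated.
- **Exclusions would be partly visible.** Section 11 reports N for each clinical and tolerability parameter at each time point, so a fall in numbers would show. The reasons would not.
- **Inflated efficacy is the tempting stronger reading, and the documents do not support it as the main risk.** Change is measured from before surgery. A subject graded 0 then cannot improve, and a remaining wound pushes scores up. A true mean change of zero is a convenient assumption; under a real rise, false improvement is negligible.
- **A reader might take Section 6.5.2 as a second free choice over efficacy data.** It is not. The discretion there is over whether the subject continues, and the safety-only consequence is fixed. Prohibited therapies are also limited to those in the eligibility criteria, so another topical product on the wound does not clearly fall under it. What remains is that Section 11 does not say how such data are handled, or whether tolerability scores count as safety.
- **The study is small and largely descriptive.** True, but Section 11 also specifies tests at 0.05 and a safety interpretation, so the choice of who is analysed still matters.

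**Conclusion.** The point holds as a gap in safeguards. The role that grades the wound decides exclusions, with the grades available and no threshold, and Section 11 fixes neither an analysis set nor a denominator. Confidence in that reading of the text is high.

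The consequence is possible, not certain: exclusions unrelated to outcome would cause no such bias, and nothing in the documents shows that outcome-related exclusion would happen. The clearest exposure is tolerability, where one to three exclusions can turn a significant increase into a finding read as safety, depending on the test and the assumed data. The simulations that drop the worst subjects are upper-end illustrations for the number dropped. Inflation of false improvement is modest in the mild cases (0.030 to 0.037 against 0.025) and arises only if the true change from pre-procedure is about zero. This is a cheap improvement rather than a fatal flaw.

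**What to change.** 1. Replace the last sentence of Section 7.6 with: *All subjects who receive at least one application are included in the main analysis with all available data, regardless of compliance.* Name this set in Section 11.
2. For percent improved and percent worsened, report the count over subjects with a baseline grade and a grade at that visit. Beside it give the number treated and the number missing with reasons, including discontinuation for lack of efficacy, adverse event or protocol violation (Section 9.2). Without this, outcome-related loss would continue through dropout. Note that the graded denominator raises both percentages.
3. State in Section 11 how data from subjects who continue under Section 6.5.2 enter the efficacy and tolerability summaries, so that the two sections and the new sentence in 7.6 are reconciled.
4. Allow a compliant-subject analysis only as a sensitivity analysis, with a diary and product-weight criterion fixed in advance and applied without sight of the grades. List every exclusion with its reason.

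The cost is wording in three sections, one extra table with a listing, and possibly less favourable reported figures. No visit or assessment changes.

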8. TREATMENT OF SUBJECTS

8.1 Informed Consent Form

An IRB-approved informed consent form (ICF), consistent with the requirements in 21 Code of Federal Regulations (CFR) 50.25, will be given to each prospective subject. Prospective subjects will be given as much time as needed to read the ICF and will have the opportunity to have any study-related questions answered to their satisfaction prior to signing the ICF. If further questions exist, prospective subjects will be given sufficient time during the first visit to have questions regarding the study and/or the ICF answered by the Investigator, or clinic staff prior to signing.

8.2 Subject Identification

Enrolled subjects will be assigned a 3-digit subject number when used in conjunction with their initials. This will uniquely identify every subject on the study. These numbers will remain with the subjects throughout the study and should be used in all references to the individual in this study. No subject number will be reassigned once the study begins.

8.3 Subject Instructions

Subjects will be provided with the following instruction to follow upon the surgical procedure completion:

8.3.1. Post-procedure Instructions

- Keep procedure/surgical bandage in place for 36-48 hours. Remove and clean incision with warm soapy water or half-strength peroxide as needed. Do not submerge in water. Pat dry with clean towel. Limit strenuous activity.

Protocol Version 1:

This document contains confidential, proprietary information.

8.3.2. Treatment Product Usage Instruction:

- Apply the provided treatment product liberally to the surgical site at least twice a day. Reapply as needed throughout the day. Apply bandage as needed.

8.3.3. Subject Instructions for Study Visits

- Bring the treatment product and daily diary with you to every visit.

8.3.4. General Study Instructions

- Avoid extended periods of sun exposure for the duration of the study.
- Do not use any topical products (except sunscreen as needed) on the surgical site other than the provided treatment product for the duration of the study.

9. STUDY PROCEDURES

The table below represents a summary of the study procedures and evaluation schedule:

1. Visit 1 – Screening
2. Visit 2 – Baseline/Day 0 (surgical procedure)
3. Visit 3 – Day 7 (for head/neck group) or Day 14 (for body group)
4. Visit 4 – Day 28

Test design / flow chart	Visit 1	Visit 2		Visit 3	Visit 4
	Screening	Baseline Day 0 Pre-procedure	Baseline Day 0 Post-procedure	Day 7 or Day 14	Day 28
ICF and qualification/enrollment	X				
Photo consent	X				
Demographics/Med History	X				
Concomitant Meds.	X				
Inclusion and exclusion criteria	X				
CRF		X	X	X	X
Investigator grading		X	X	X	X
Subjective tolerability grading		X	X	X	X
Standardized photography		X	X	X	X
Self-assessment questionnaire				X	X
AE reporting			X	X	X
Treatment product		W	D	W	C/W
Daily diaries			D	C/D	C

For treatment product and/or daily diaries: W = Weigh, D = Distribute, C = Collect

Protocol Version 1:

This document contains confidential, proprietary information.

Protocol GLI.04.US.SL.017

CONFIDENTIAL

9.1 Visits and Examinations

9.1.1. Visit 1 (Screening)

1. Subjects will report to the clinic for screening to determine if they are eligible to be in the study.
2. Prior to beginning of any study related activities, subjects will be informed about the purpose and nature of the study, the expected post-procedure events, and the potential risks involved with the surgical procedure and treatment product.
3. Subjects will be given an ICF, HIPAA form, and photography release form to read.
4. Once subjects have completed reading, they will be interviewed to ensure their understanding of the aforementioned forms and be given the opportunity to ask any study related questions.
5. Subjects who agree to sign the aforementioned forms will be asked to complete a demographic information, medical history form, and concomitant medication form. Subjects declining to sign any of the forms will be dismissed from the study.
6. Subjects will be screened and qualified on the basis of the subject inclusion and exclusion criteria. Subjects failing to meet criteria will be dismissed from the study.

9.1.2. Visit 2 (Baseline/Day 0 – Surgical procedure)

1. Investigator or clinic staff will ask the subjects if they have experienced any changes in their health since the previous visit.
2. Before the surgical procedure, the assessments below will be completed:
 - a. Clinical grading by Investigator as described in section 10.1
 - b. Tolerability assessment by the subjects as described in section.
3. The surgical area will be assessed and prepped for the procedures, followed by procedure execution by Investigator.
4. After the surgical procedure, the assessments below will be completed:
 - a. Standardized photography as described in section 10.3
 - b. Clinical grading by Investigator as described in section 10.1
 - c. Tolerability assessment by the subjects as described in section 10.2
5. Investigator or clinic staff will apply the treatment product to the surgical site followed by standard bandage.
6. Subjects will be given the treatment product with instruction of application, a diary to record usage of the treatment product, and when to contact the Investigator in case of emerging AEs.
7. Subjects will be scheduled for a follow-up visit at Day 7 or 14 (± 2 days) and dismissed from the Clinic.

9.1.3. Visit 3 (Day 7 or Day 14 ± 2 days)

1. Clinic staff or Investigator will record any AEs that are observed or reported.
2. The surgical site will be assessed in the following:
 - a. Clinical grading by Investigator as described in section 10.1
 - b. Tolerability assessment by the subjects as described in section 10.2
 - c. Standardized photography as described in section 10.3
 - d. Self-assessment questionnaire as described in section 10.4
3. Clinic staff or Investigator will collect and review the treatment product and diary for compliance purpose.

Protocol Version 1:

This document contains confidential, proprietary information.

4. Subjects will be scheduled for a follow-up visit at Day 28 (± 3 days) and dismissed from the Clinic.

9.1.4. Visit 4 (Day 28 ± 3 days)

1. Clinic staff or Investigator will record any AEs that are observed or reported.
2. The surgical site will be assessed in the following:
 - a. Clinical grading by Investigator as described in section 10.1
 - b. Tolerability assessment by the subjects as described in section 10.2
 - c. Standardized photography as described in section 10.3
 - d. Self-assessment questionnaire as described in section 10.4
3. Clinic staff or Investigator will collect and review the treatment product and diary for compliance purpose.
4. Once completed, subjects will be dismissed from the Clinic.

9.2 Discontinued Subjects

Any subject is free to discontinue his/her participation in this study at any time and for whatever reason, specified or unspecified, and without prejudice.

Investigator may decide to discontinue a subject from the study for safety reasons or when it is in the best interest of the subject. Galderma Laboratories, L.P. may also decide to prematurely terminate or suspend the study or the participation of a subject in the study. All data gathered on the subject prior to termination should be made available to Galderma Laboratories, L.P.

Criteria for the discontinuation of a subject during the study will include the following:

- Adverse Event
- Lack of Efficacy
- Pregnancy
- Subject Request
- Protocol Violation
- Lost to Follow-up
- Any unmanageable factor, in the Investigator’s opinion, that may significantly interfere with the protocol or interpretation of results.

10. STUDY ASSESSMENTS

All data and images taken from the study will be saved and shared to the Sponsor via a data-protected platform.

10.1 Clinical Grading by Investigator

Investigator will perform clinical grading at the surgical site on each subject at baseline (pre- and post-procedure), day 7/14, and day 28. Investigator will grade the severity of wound parameters based on a visual analog scale, described in the table below (for erythema, edema, overall wound appearance, half-point scores can be used as necessary to better describe the condition):

Parameters	Score 0	Score 1	Score 2	Score 3
Erythema	None/absent	Mild	Moderate	Severe

Protocol Version 1:

This document contains confidential, proprietary information.

Edema	None/absent	Mild	Moderate	Severe
Overall wound appearance	Excellent (absent of wound)	Good (slightly visible wound)	Fair (moderately visible wound)	Poor (marked visible wound)

Parameters	Score 0	Score 1	Score 2	Score 3	Score 4
Scabbing/crusting	None	Slight (up to 30%)	Moderate (31-60%)	Extensive (61-90%)	Almost complete or complete (91-100%)

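### Scabbing/crusting is graded as a percentage of an unnamed area and tested against a pre-procedure score from which, when it is 0, no improvement is possible

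*Combined protocol and SAP*

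**What the plan says.** Section 10.1 lists four investigator grades. Erythema, edema and overall wound appearance are graded in words. Scabbing/crusting alone is graded by percentage, with score 1 as "Slight (up to 30" per cent) and score 4 as "Almost complete or complete (91-100" per cent). No reference area is named. The nearest anchor is "Investigator will perform clinical grading at the surgical site on each subject", which gives a location but not an area. The overall-appearance scale in the same section runs down to "Excellent (absent of wound"), so the plan allows for a wound that shrinks and disappears.

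Section 9.1.2 has the grading done before the procedure and again after it ("After the surgical procedure, the assessments below will be completed"), the second time before the ointment is first applied.

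Section 11 takes the pre-procedure score as baseline. The test is of "The null hypothesis, that the mean change from baseline (pre-procedure) is zero", by paired t-test, or by Wilcoxon signed-rank test if normality fails. Each parameter also gets a percent mean change, with the pre-procedure mean as divisor, and a percentage based on the "number of subjects improved/worsened from baseline preprocedure". For clinical grading as a whole the stated reading is "A decrease in scores indicates an improvement". Crusting has no exception.

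**The concern.** There are two separate problems.

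The first is the denominator. A percentage needs a reference area, and this one could be the original wound or whatever wound is left at the visit. As a wound shrinks the two diverge, so identical sites can get different scores. The synopsis describes a multi-center study, section 6.2 mixes Mohs surgery, biopsy and excision, and no grading convention or grader training is described.

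The second is the reference time. The baseline score is taken before the surgical wound exists. If crusting is 0 at that point, the score can only stay level or rise. The planned test, percent change and improved/worsened counts then cannot show benefit on this parameter. They can only show no change or harm, whatever the ointment does.

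At stake is whether one of the four investigator grades can be interpreted.

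**Working it through.** The documents give no expected crusting score, effect size or power figure, so there is no stated number to reproduce.

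**Denominator.** Let f be the remaining wound as a fraction of the original, and c the crusted fraction of the remaining wound. With the remaining wound as reference, the section 10.1 bands apply to c. With the original wound as reference, they apply to f × c. The values of f and c are illustrative, because the documents give no wound areas.

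| f | c | Score, remaining wound | f × c | Score, original wound |
|---|---|---|---|---|
| 1.00 | 1.00 | 4 | 1.00 | 4 |
| 0.80 | 1.00 | 4 | 0.80 | 3 |
| 0.40 | 1.00 | 4 | 0.40 | 2 |
| 0.30 | 1.00 | 4 | 0.30 | 1 |
| 0.10 | 1.00 | 4 | 0.10 | 1 |
| 0.80 | 0.50 | 2 | 0.40 | 2 |

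A split of 4 against 1 needs c ≥ 0.91 and f × c ≤ 0.30, so f ≤ 0.30/c. That limit is 0.30 at c = 1.00 and 0.30/0.91 = 0.33 at c = 0.91. At the light end there is no gap: with c = 0.20 both readings give 1 at every f checked from 0.05 to 1.

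The trend can also reverse. Take a site at f = 0.80, c = 0.50 at Visit 3 and f = 0.10, c = 1.00 at Day 28. It goes from 2 to 4 on the remaining wound but from 2 to 1 on the original wound, while the crusted area falls from 40% to 10% of the original.

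**Reference time.** Assume all 20 subjects score 0 before the procedure, k of them score 1 at a later visit, and the rest stay at 0.

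- Paired t-test: mean change = k/20, s² = (20/19)(k/20)(1 − k/20), t = mean/(s/√20) on 19 degrees of freedom.
- Exact signed-rank test with zeros dropped: all k changes are positive, so two-sided p = 2 × 0.5^k.
- k = 4: mean 0.20, s = 0.410, t = 0.20/0.0918 = 2.18, p = 0.042; signed-rank p = 0.125; 20% worsened.
- k = 5: t-test p = 0.021; signed-rank p = 0.0625; 25% worsened.
- k = 6: mean 0.30, s = 0.470, t = 0.30/0.105 = 2.85, p = 0.010; signed-rank p = 0.031; 30% worsened.

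So 4 subjects with the lowest grade of crust reach significance on the t-test, and 6 do so on either test. In each case 0% can be counted as improved. The percent mean change is (visit mean − 0)/0, which is undefined.

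The two problems are independent. Fixing the denominator settles the first table, but any crust after a baseline of 0 would still be an increase.

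**The case against.** The best defence on the denominator is that grading at the surgical site points to a fixed place. Section 10.3 uses the same term for photographs taken at every time point in the same position and at the same camera distance, and no section names the remaining wound as the graded unit. This stands in part: the fixed-area reading is the more natural one. But the area is still undefined.

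A reader might infer that a nearly healed site will typically be scored 1 by one grader and 4 by another, or that half the sites would be graded each way. The documents do not support either. The 1-against-4 split is the extreme case worked out above, and the shrinkage model may not fit every wound, since section 8.3.1 speaks of an incision and the method of closure is not given. The numbers of centers and graders are not stated, so no split between conventions can be derived.

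A reader might also infer that crust is a normal stage of healing, so that the scale runs backwards. No section says so. Section 4 sets out a moist, occlusive wound environment as the aim, which fits treating crust as unfavourable. The direction of the scale can therefore stand.

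On the baseline, pre-procedure scores are not given, and a lesion already crusted before surgery could score above 0, so worsening is not automatic for every subject. It is also fair to say that a pre-procedure reference is awkward for all four grades. Crusting differs in that the obvious substitute, the Day 0 post-procedure grade, may not help: if crust has not yet formed by then (an assumption), that score is also near 0.

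**Conclusion.** The concern holds within limits. The crusting percentage has no stated reference area, and the choice can shift the score of a heavily crusted site by 0 to 3 grades depending on how far the wound has shrunk, with 3 grades only when about 30% or less remains. Separately, for any subject with a pre-procedure crusting score of 0, section 11 makes improvement impossible and counts any later crust as worsening. A zero baseline mean leaves the percent change undefined. The p values above assume a score of 0 in all 20 subjects. A baseline of 0 is probably common but is not documented.

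The point should be corrected, but its reach is modest. It concerns one of four investigator grades in an uncontrolled study of 20 completers with no named primary endpoint, and no decision rule depends on crusting. It does not show that the scale runs against healing.

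**What to change.** In section 10.1, define the crusting percentage as crusted area divided by the original wound area at Day 0, judged by eye against the post-procedure photograph already taken, and apply it at every follow-up visit. Section 10.3 mentions no scale marker, so this is a visual estimate rather than a measurement.

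In section 11, for crusting only, drop the test against the pre-procedure score, the percent mean change and the improved/worsened counts. Replace them with:

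- the distribution of scores and the percentage of subjects at score 0, at Visit 3 and at Day 28;
- within-subject change from Visit 3 to Day 28, reported separately for head/neck (Day 7 to 28, nominally 21 days) and body (Day 14 to 28, nominally 14 days), because pooling would mix the two intervals.

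Keep a lower score as the more favourable one.

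The cost is a line in the grading table and one table shell, with no new visit or procedure. Graders must consult the Day 0 photograph, crusting no longer yields a p value for change from Day 0, and each change summary rests on the 10 completers planned per body region.
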